## 2.4 STATISTICAL METHODS

### 2.4.1 Demographics and baseline characteristics

Continuous data will be summarized using the number of observations available, mean, SD, median, minimum, and maximum for each treatment group. Categorical and ordinal data will be summarized using the count and percentage of patients in each treatment group.

Parameters will be summarized based on the randomized population analyzed in the treatment group to which they were randomized. Analyses for the safety population will be included in the appendices if the size of the safety population is different (>10%) from the size of that in the primary analysis population (ie, randomized patients) for any treatment group.

Parameters described in [Section 2.1.1](#) will be summarized by treatment group and overall (pooled across treatment groups) using descriptive statistics.

P-values on the treatment difference for the demographic and baseline characteristic data will not be calculated.

In general, no specific description of the safety parameters will be provided at baseline. If relevant, the baseline values will be described along with each safety analysis.

In general, no specific description of the efficacy parameters will be provided at baseline. If relevant, the baseline values will be described along with each efficacy analysis.

## 2.4.2 Prior or concomitant medications

The prior, concomitant and posttreatment medications will be presented in the randomized population for each treatment group (and overall for the summary of prior medications), using counts and percentages. No statistical test for the between-group difference will be performed.

Medications will be summarized by treatment group according to the WHO-DD dictionary, considering the first digit of the anatomical therapeutic chemical (ATC) class (anatomic category) and the first 3 digits of the ATC class (therapeutic category). A given medication may be classified in more than 1 ATC class. All ATC codes corresponding to a medication will be summarized, and a patient will be counted once within each ATC category (anatomic or therapeutic) linked to the medication. Therefore a patient may be counted several times for the same medication.

Prior medications will be presented by anatomic and therapeutic categories and sorted by decreasing frequency of ATC based on the overall incidence across treatment groups. In case of equal frequency regarding ATCs (anatomic or therapeutic categories), alphabetical order will be used.

Concomitant and posttreatment medications will be presented by anatomic and therapeutic categories and sorted by decreasing frequency in the sotagliflozin 400 mg group. In case of equal frequency regarding ATCs (anatomic or therapeutic categories), alphabetical order will be used.

## 2.4.3 Extent of investigational medicinal product exposure and compliance

The extent of IMP exposure and compliance will be assessed and summarized by actual treatment within the safety population ([Section 2.3.2](#)).

### 2.4.3.1 Extent of investigational medicinal product exposure

The extent of IMP exposure will be assessed by the duration of IMP exposure.

Duration of IMP exposure is defined as last dose date of double-blind IMP – first dose date of double-blind IMP + 1 day, regardless of unplanned intermittent discontinuations (see [Section 2.5.3](#) for calculation in case of missing or incomplete data). Duration of IMP exposure will be summarized descriptively as a quantitative variable (number of patients exposed, mean, SD, median, minimum, and maximum). In addition, duration of treatment exposure will also be summarized categorically by numbers and percentages for each of the following categories and cumulatively according to these categories:

- 1 to 28 days,
- 29 to 56 days,
- 57 to 84 days,
- 85 to 126 days,
- 127 to 182 days,

- 183 to 364 days,
- 365 to 551 days,
- >551 days.

Additionally, the cumulative duration of treatment exposure will be provided, defined as the sum of the duration of treatment exposure for all patients, and will be expressed in patient years.

Number and percentage of patients by final dose at the end of the treatment will also be presented by each treatment group.

#### **2.4.3.2 Compliance**

A given administration will be considered noncompliant if the patient did not take the planned dose of treatment as required by the protocol. No imputation will be made for patients with missing or incomplete data.

Percentage of compliance for a patient will be defined as the number of days that the patient was compliant divided by the total number of days that the patient was planned to take during the treatment epoch defined in [Section 2.1.4](#) (ie, from the first date to the last date of double-blind IMP administration).

Above-planned dosing percentage for a patient will be defined as the number of days that the patient took a higher dose than planned divided by the total number of days that the patient was planned to take during the treatment epoch.

Under-planned dosing percentage for a patient will be defined as the number of days that the patient took a lower dose than planned divided by the total number of days that the patient was planned to take during the treatment epoch.

Treatment compliance, above-planned, and under-planned dosing percentages will be summarized descriptively as quantitative variables (number, mean, SD, median, minimum, and maximum). The percentage of patients whose compliance is <80% will be summarized. In addition, numbers and percentages of patients with at least 1 day above-planned dose administration will be provided, as well as numbers and percentages of patients with (0, 20%], and >20% of days under-planned dose administrations.

Cases of overdose (see study protocol for further details) will constitute AEs/SAEs and be analyzed as such. More generally, dosing irregularities will be listed in [Section 2.2.1](#).

#### **2.4.4 Analyses of efficacy endpoints**

Efficacy analyses will be performed on the ITT population using the efficacy assessments collected during the study, including those obtained after IMP discontinuation or introduction of rescue therapy, unless otherwise specified.

Statistical testing will be performed for primary endpoint and some secondary endpoints at Week 26 (or Week 12 for SBP) as specified in following subsections. All efficacy variables after Week 26 will only be summarized by descriptive statistics without formal statistical testing.

Missing data for efficacy analyses is identified through steps described in [Section 2.5.4](#).

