### 1.2.3 Other objectives

[figure not shown]
- To compare sotagliflozin versus placebo based on other blood pressure endpoints.
- To compare sotagliflozin versus placebo with respect to change from Baseline on the following endpoints:
  - Estimated glomerular filtration rate (eGFR),
  - Reduction in body weight by  $\geq 2\%$ ,  $\geq 5\%$ , and  $\geq 10\%$ .
- To compare sotagliflozin versus placebo for:
  - Change from Baseline in HbA1c at Week 79,
  - Change from Baseline in FPG at Week 79,
  - Change from Baseline in body weight at Week 79.
- To compare the use of rescue medications for hyperglycemia in the sotagliflozin and placebo treatment groups.
- To assess plasma concentrations of sotagliflozin and its 3-O-glucuronide metabolite.

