**Table 1 - Protocol amendment statistical changes**

Amendment Number	Date Approved	Rationale	Description of statistical changes
2	20-Dec-2017	5 half-lives of sotagliflozin prolonged to 10 days considering patients with moderate renal dysfunction	5 half-lives of IMP updated from 5 days to 10 days; TEAE period updated accordingly
2	20-Dec-2017	Baseline eGFR defined as recommended by CDISC Therapeutic Area Data Standards User Guide for Diabetic Kidney Disease	For serum creatinine and eGFR, the baseline value is defined as the average of all values before the first dose of double-blind IMP for those randomized and exposed or before randomization for those who were randomized but never exposed to IMP.
2	20-Dec-2017	The effect in body weight is considered more closely associated with the planned indication	Change in the order of secondary objectives, endpoints and multiplicity considerations
2	20-Dec-2017	Urgent coronary revascularization not adjudicated by CEC to be consistent with outcome trials	Urgent coronary revascularization not included in adjudication related analyses
2	20-Dec-2017	AE leading to study discontinuation is less clinically relevant than AE leading to treatment discontinuation	Delete AEs leading to discontinuation from the study from safety endpoints
2	20-Dec-2017	To understand treatment effects over the entire study duration	Several objectives/endpoints "blood pressure endpoints at Week 26 and Week 79, HbA1c, FPG and body weight endpoints at Week 79" were added

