### 2.1.3 Efficacy endpoints

All efficacy measurements collected during the study will be considered for analyses, including those obtained after IMP discontinuation or introduction of rescue therapy (see [Section 2.5.4](#)).

HbA1c, FPG, serum creatinine, eGFR are measured/calculated in a central laboratory (see study flowchart in [D](#)). Body weight, SBP and diastolic blood pressure (DBP) (see [Section 2.1.4.5](#)) are measured at on-site visits by the investigator. Patients requiring rescue are identified as those with the reason for treatment ticked “rescue therapy” in e-CRF “Medication” page.

Efficacy variables will be summarized in both standard international units and conventional units when applicable.

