Results from each analysis will be combined using Rubin's formula, to provide the adjusted mean change in HbA1c from baseline to Week 26 (or Week 12 for SBP) for each treatment group, as well as the between-group difference (comparing sotagliflozin 400 mg versus placebo) and its associated 95% confidence interval (CI).

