### **2.4.4.3 Analyses of other efficacy endpoints**

The analysis of other endpoints (see [Section 2.1.3](#)) will be descriptive with no formal testing. Summary statistics at scheduled visits based on observed value will be provided by each treatment group. Graphical presentations will also be used to illustrate trends over time as appropriate.

The number (%) of patients who used rescue therapy will be summarized by treatment group during the core (see [Section 2.5.4](#)) and the entire double-blind treatment periods. A KM curve for the time to first rescue therapy will be provided by treatment group. A list of patients who used rescue therapy will also be provided (see [Section 2.5.4](#)).

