### ***Summary statistics by visit for continuous efficacy endpoints***

Summary statistics (number, mean, SD, SE, minimum, median, maximum) of continuous efficacy endpoints (observed data and change from baseline) will be provided at scheduled visits as per protocol. Summaries showing data by visit will be presented according to the visit number (or re-allocated visit number) and labeled with the targeted approximate day/week.

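### The Week 79 objectives are to compare the arms, but the plan prespecifies only per-arm observed-case summaries, with no between-arm difference, confidence interval, adjustment or missing-data method

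*SAP*

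**What the plan says.** **Objectives.** SAP 1.2.3, like protocol 5.3, sets the aim "To compare sotagliflozin versus placebo for" a list that includes "Change from Baseline in HbA1c at Week 79", with FPG and body weight at the same visit. SAP 2.1.3.3 also lists Week 79 change in SBP, for all patients and for those with baseline SBP of at least 130 mmHg. SAP Table 1 records that these items came in with Protocol Amendment 2, and gives the reason: "To understand treatment effects over the entire study duration".

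**Analysis.** SAP 2.4.4 states: "All efficacy variables after Week 26 will only be summarized by descriptive statistics without formal statistical testing". Protocol 11.4.2 has the same rule. For the other endpoints, SAP 2.4.4.3 adds: "Summary statistics at scheduled visits based on observed value will be provided by each treatment group". The by-visit statistics for continuous endpoints (SAP 2.5.4) are number, mean, SD, SE, minimum, median and maximum, and mean plots with SE bars are planned.

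**Data used.** SAP 2.1.3: "All efficacy measurements collected during the study will be considered for analyses, including those obtained after IMP discontinuation or introduction of rescue therapy". For HbA1c only, SAP 2.4.4.1 repeats the by-visit presentation without post-rescue values through Week 79. SAP 2.4.4.3 gives rescue counts and a Kaplan-Meier curve by arm.

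**The concern.** A treatment effect is a contrast between arms. The stated reason for adding the Week 79 endpoints is to learn about treatment effects over the whole study, yet the planned output stops at one summary per arm. Declining to test does not require dropping the estimate, its interval, the covariate adjustment or the treatment of missing data.

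The extension is 53 of the 79 treatment weeks. If the contrast is not prespecified, whatever Week 79 difference is later quoted will have been chosen after the data are seen. It will also rest on whoever happens to have a Week 79 value. At Week 26 the SAP judged missing data serious enough for a retrieved-dropout imputation, a washout back-up and a tipping-point analysis. A year later there is nothing equivalent.

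The HbA1c display without post-rescue values does not fill the gap. Extension rescue is triggered by FPG above 170 mg/dL or HbA1c of at least 8.0% (protocol 8.2.2), so that display removes values according to the patient's own glycaemia.

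**Working it through.** **1. The plan's own figure.** Inputs from SAP 1.3 and protocol 11.1: SD 1.2, 250 per arm, difference 0.6, two-sided alpha 0.05.

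- SE of the difference = 1.2 × √(2/250) = 0.1073.
- 0.6 / 0.1073 = 5.59, and power = Φ(5.59 − 1.96) = 99.99%.

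This agrees with 99% in the SAP and at least 99% in the protocol; 147 per arm would give 99%. The figure is for Week 26. Neither document gives one for Week 79.

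**2. What is specified at each time point.**

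| Element | Week 26 (Week 12 for SBP) | Week 79 |
|---|---|---|
| Between-arm difference with 95% CI | Yes (SAP 2.4.4.1, 2.4.4.2) | None |
| Adjustment for baseline, strata, country | Yes, ANCOVA | None |
| Missing-data method | Retrieved-dropout or washout imputation | None |
| Per-arm summaries on observed values | Yes | Yes |

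SAP Appendix C adds no model or contrast for Week 79 and has no separate row for Week 79 HbA1c, FPG or weight. SAP 2.5.4 mentions multiple imputation for values still missing after visit windowing, but refers back to SAP 2.4.4, where the imputation is written only for Week 26 or Week 12.

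**3. What *descriptive* means elsewhere in this SAP.**

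- The subgroup analyses in SAP 2.4.4.1 are labelled descriptive. They still use the primary imputation and ANCOVA, and report adjusted differences with SE and 95% CI.
- Safety analysis is described as essentially descriptive, yet relative risks with 95% CIs may be given (SAP 2.4.5).
- HbA1c below 6.5% is outside the testing hierarchy (SAP 2.4.4.4), yet gets a difference with a CI (SAP 2.4.4.2).

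An untested Week 79 difference with a CI would fit this practice.

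**4. What a reader could derive.** From the planned output, SE(difference) = √(SE₁² + SE₂²). At SD 1.2:

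- 250 per arm: each SE = 1.2/√250 = 0.0759, so SE(difference) = 0.107.
- 150 per arm: each SE = 1.2/√150 = 0.0980, so SE(difference) = 0.139.

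**5. Precision of a Week 79 HbA1c difference.** Half-width = 1.96 × SD × √(2/n). The SD is carried over from Week 26, and the number observed is an assumption (60% to 100% of 250).

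| Observed per arm | 250 | 225 | 200 | 175 | 150 |
|---|---|---|---|---|---|
| SD 1.0 | 0.175 | 0.185 | 0.196 | 0.210 | 0.226 |
| SD 1.2 | 0.210 | 0.222 | 0.235 | 0.251 | 0.272 |
| SD 1.4 | 0.245 | 0.259 | 0.274 | 0.293 | 0.317 |

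These are unadjusted values. They show that the trial is large enough for a useful estimate.

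**6. Illustration of ignoring missing values.** Every input here is assumed. An arm's observed mean is too favourable by (share missing) × (how much worse the missing patients are).

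- Placebo: 0.20 × 0.4 = 0.08 up to 0.30 × 0.6 = 0.18.
- Sotagliflozin: 0.20 × 0.2 = 0.04.
- Net: 0.08 − 0.04 = 0.04 up to 0.18 − 0.04 = 0.14 points, or 7% to 23% of 0.6.

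In this example placebo looks too good, so the observed difference understates the benefit of sotagliflozin. Other inputs could reverse the direction.

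**The case against.** The strongest reply is that this is deliberate. Week 79 HbA1c, FPG and weight sit in the lowest tier of objectives. Protocol and SAP agree that efficacy after Week 26 is descriptive and untested, and setting two arms side by side is a comparison of a kind. That stands as far as testing goes: the absence of a p-value is not an error, and the documents do not contradict each other on it. It does not explain the missing estimate, because this SAP attaches adjusted differences and intervals to other analyses that it calls descriptive.

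A reader might infer that the trial cannot answer its Week 79 objectives. The documents do not support that. Both arms are followed, the planned means and SEs yield an unadjusted difference and CI, and the sample is large enough. The gap is in specification and reporting.

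A reader might also take the planned figures for completer means. They are observed-case means in the ITT population. Values after treatment discontinuation and after rescue count, and patients who stop early are asked back, particularly for Week 79 (protocol 6.1.3). Unscheduled values from Day 503 can be re-allocated to Week 79 (SAP 2.5.4). All this reduces the missing-data problem without removing it.

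The bias illustration is not evidence of a real bias. Its inputs are free choices, its direction in the example is against sotagliflozin, and its size is below the CI half-width.

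**Conclusion.** The concern holds as a mismatch between objective and analysis. The Week 79 objectives call for a comparison, and the plan prespecifies no between-arm estimate, interval, adjustment or missing-data handling for them. What can be derived from the planned tables would be unadjusted and post hoc, and would ignore missing Week 79 values.

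The consequence is limited to exploratory objectives; the primary and secondary conclusions and the alpha hierarchy are untouched. A prespecified HbA1c difference would carry a 95% half-width of about 0.21 to 0.27 points, assuming that SD 1.2 still applies at Week 79 and that 150 to 250 patients per arm are observed. Over SDs of 1.0 to 1.4 the range is about 0.18 to 0.32. The size of any bias from missing data cannot be settled from the documents.

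**What to change.** In SAP 2.4.4.3, with matching changes to protocol 11.4.2 and 11.4.2.3, prespecify for Week 79 HbA1c, FPG, body weight and SBP the Week 26 ANCOVA with multiple imputation. The imputation text cannot be reused unchanged, because it is tied to Week 26 and Week 12. It needs three changes:

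- Define retrieved dropouts as patients who stop study drug before Week 79 but have a Week 79 value.
- Re-apply the fewer-than-5 switch to the back-up method at Week 79, endpoint by endpoint.
- Include the extension visits in the back-up model.

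For SBP in patients with baseline SBP of at least 130 mmHg, omit the SBP stratum, as is already done at Week 12. Report the adjusted difference with its 95% CI, labelled descriptive, without a p-value and outside the hierarchy. Keep the observed-case tables as support. To count as prespecified, the text must be in place before unblinding.

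The cost is a short SAP paragraph, the matching protocol wording and modest extra programming. No new data, patients or alpha are needed. The minimum alternative is to change the objective from *compare* to *describe*, but that gives up the purpose for which the Week 79 endpoints were added.

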#### **2.4.4.1 Analysis of primary efficacy endpoint**

The statistical test will be two-sided tests at a nominal 5% significance level.

##### **Primary analysis**

The primary efficacy endpoint of change in HbA1c from baseline to Week 26 will be analyzed by an Analysis of Covariance (ANCOVA) model using HbA1c values measured at baseline and Week 26 (observed or imputed). The missing data at endpoint will be imputed by multiple imputation [MI] methods as detailed below. To be concise, the following texts related to imputation are generalized to accommodate primary as well as continuous secondary efficacy endpoints.

Missing endpoint data at Week 26 (or Week 12 for SBP) visit will be imputed using a model built separately in each treatment group and estimated from the patients in the same treatment group who prematurely discontinue the IMP before the Week 26 (or Week 12 for SBP) visit but have the measurement for the endpoint (ie, retrieved dropouts). The imputation model will include the randomization strata and the corresponding baseline value. In cases of non-convergence during the imputations, the offending stratum will be identified and then will be dropped from the model. Considering that the number of retrieved dropout patients in each treatment group is expected to be small, a simple imputation model based on regression will be used with baseline measurement included as the predictor. This will serve as the primary method of imputation for missing data should sampling criteria be satisfied (see below).

An alternative (back-up) imputation method will be used if the number of patients who prematurely discontinue the IMP before the Week 26 (or Week 12 for SBP) visit but have the measurement for the endpoint is  $< 5$  in any treatment groups (ie, an insufficient number of retrieved dropouts to support the imputation method described above). This criterion will be assessed for each primary and continuous secondary efficacy endpoint.

In the back-up imputation method, missing post-baseline endpoint values at Week 26 (or Week 12 for SBP) will be imputed by the washout Multiple Imputation (MI) method under the missing not at random (MNAR) framework.

Missing endpoint data at the Week 26 (or Week 12 for SBP) in all treatment groups (sotagliflozin 400 mg and placebo) are imputed from a model estimated from patients in the placebo group who have the endpoint data available.

For patients in the sotagliflozin 400 mg group with missing data at Week 26 (or Week 12 for SBP), their missing values will be imputed using observed baseline and the observed primary endpoint data from placebo completers; no intermittent values from either placebo or the active treatment groups will be used.

For placebo patients, missing data will be imputed based on the placebo group data. Intermittent observed values will be used while imputing missing values at Week 26 (or Week 12 for SBP). In cases that a non-monotone missing data pattern occurs at the intermediate visits, these data points will be first imputed in the placebo group using the Markov Chain Monte Carlo (MCMC) option in PROC MI to achieve a monotone missing pattern for all placebo patients. The Week 26 (or Week 12 for SBP) endpoint values will be subsequently imputed from the multiple copies of the original dataset where each copy will have a monotone missing pattern.

The imputation models for the washout MI method will include the randomization strata and the corresponding baseline value. Missing data will be imputed using the regression method.

In cases of non-convergence during the imputations, especially for the MCMC application in the placebo non-monotone datasets, graphical measures (eg, trace and autocorrelation plots) will be used to identify the offending variable and once detected, that variable(s) will be dropped from the model and the imputations will be re-run. These re-run models will use the same seed number and number of imputations as used in the original models.

Using either imputation method, missing endpoint data will be imputed 2000 times to generate multiple data sets with complete data. Other details of the imputation procedures such as the seed number and sort ordering are specified in the SAS programs. The HbA1c change from baseline to Week 26 (or Week 12 for SBP) will be derived from observed and imputed HbA1c values at Week 26 (or Week 12 for SBP).

Each of the completed datasets after the imputation will be analyzed using the Analysis of Covariance (ANCOVA) model with treatment groups (sotagliflozin 400 mg, placebo), randomization stratum of HbA1c ( $\leq 8.5\%$ ,  $> 8.5\%$ ), randomization stratum of metformin use at Screening (Yes, No), randomization stratum of SBP ( $< 130$  mmHg,  $\geq 130$  mmHg), and country as fixed factors, and baseline value of the efficacy endpoint as a covariate.

Results from each analysis will be combined using Rubin's formula, to provide the adjusted mean change in HbA1c from baseline to Week 26 (or Week 12 for SBP) for each treatment group, as well as the between-group difference (comparing sotagliflozin 400 mg versus placebo) and its associated 95% confidence interval (CI).

